### 10.3.2 TMB as Molecular Marker of Efficacy

TMB is measured in ATHENA using the FoundationOne Dx (F1CDx). The F1CDx is a next-generation sequencing (NGS) assay targeting the full coding regions of 324 genes. TMB by F1CDx is determined by counting all synonymous and non-synonymous variants present at 5% allele frequency or greater (after filtering). The resulting number is communicated as mutations per megabase unit (mut/Mb). The cutoff used for analysis will be  $\geq$  10 mut/Mb.

## 10.3.3 Progression Free Survival 2 (PFS2)

The second event of progression, PFS2, is defined as the time from randomization to the second event of disease progression as assessed by the investigator, or death due to any cause. The second event will be the disease progression event as reported during the subsequent anticancer follow up. Subsequent anticancer treatments will be collected for all patients every 12 or 24 weeks (± 14 days), until death, loss to follow-up, withdrawal of consent from study, or closure of the study. The subsequent anticancer data with start and stop date and any date of progression will be documented. The date of progression on subsequent anticancer treatments may be a documented event per RECIST guidelines or may be an event of symptomatic/clinical or CA-125 progression. Patients who have not died or had a second event of disease progression will be censored on the date the patient was last known to be alive or last visit. PFS2 will be analyzed using Cox proportional hazard methodology and a stratified log-rank test. The stratified hazard ratio (and 95% confidence interval) from the Cox proportional hazards model will be used to estimate the HR between the randomized treatment groups.

## 10.3.4 Efficacy for Arm C (nivolumab) monotherapy vs placebo

The primary and secondary efficacy endpoints will be summarized for nivolumab (Arm C) compared to placebo (Arm D). The endpoints will be analyzed as described in sections 10.1 and 10.2.

#### 10.3.5 Efficacy for Arm A (Combination) vs placebo

The Primary and secondary efficacy endpoints will be summarized for Arm A (rucaparib + nivolumab) compared to the placebo (Arm D). The endpoints will be analyzed as described in sections 10.1 and 10.2.

Confidential 35 of 52

10.3.6 Health-related Quality of Life (QoL) as assessed by the trial outcome indication (TOI) of the Functional Assessment of Cancer Therapy – Ovarian (FACT-O)

PRO utilizing the TOI FACT-O will be assessed at screening, on Day 1 (Cycle 1 through 3, and Cycle 5), then every 12 weeks (aligning with CT scans) until treatment discontinuation. In addition, PRO assessments will be performed at End of Treatment, and at the FU1 (28-day Safety Follow-up) and the FU2 (5-month Safety Follow-up) for all patients.

Patients will complete the instruments on an electronic device before any other scheduled study procedures are performed and dosing occurs (if applicable). The patient reported outcome data will be scored and summarized in accordance with the scoring manual for the questionnaire. Appendix A includes the English version of the questionnaires used with the subscale domains outlined.

Analyses of changes and/or percent changes from baseline will be analyzed for each scheduled postbaseline visit and for the final visit for each subscale, total score, and FACT-O TOI. Patients that do not have both a baseline measurement and at least one postbaseline measurement will not be included. The final visit is defined as the last assessment within 28 days after date of last dose of oral study drug or within 5 months of IV study drug, whichever is later.

For the protocol-specified post-baseline visits; the QoL assessment will be grouped in the following visit windows as described in Table 3 below.

Table 3 Algorithm for Visit Window of QoL

Visits	Visit Window Start Date	Visit Window End Date
Cycle 2 Day 1	EDC Cycle 2 Day 1 date - 3 days	EDC Cycle 3 Day 1 date - 4 days
Cycle 3 Day 1	EDC Cycle 3 Day 1 date - 3 days	EDC Cycle 4 Day 1 date + 7 days
Cycle 5 Day 1	EDC Cycle 5 Day 1 date -7 days	EDC Cycle 6 Day 1 date + 7 days
Cycle 8 Day 1	EDC Cycle 8 Day 1 date -7 days	EDC Cycle 9 Day 1 date + 7 days
Cycle 11 Day 1	EDC Cycle 11 Day 1 date -7 days	EDC Cycle 12 Day 1 date + 7 days
Cycle 14 Day 1	EDC Cycle 14 Day 1 date -7 days	EDC Cycle 15 Day 1 date + 7 days
Etc		
Cycle X Day 1,		
(where X is every 3 cycles)	EDC Cycle X Day 1 date -7 days	EDC Cycle (X+1) date + 7 days

If more than one assessment falls within a given visit window, the one that is closest to the actual scheduled EDC visit date will be used. In the case of ties, the assessment prior to the scheduled visit date will be used. The data sets should highlight the value for the patient that

Confidential 36 of 52

was included in the summary table, wherever feasible. The summary tables and graphs will only display data if the number of observations is greater than 10 in each treatment arm.

At a given visit, the change from baseline will be analyzed for the treatment comparisons using an Analysis of Covariance (ANCOVA) with treatment and stratification variables as categorical factors and baseline measurement for the parameter as a continuous covariate. In addition, a graphical presentation of mean changes over time may be presented.

In addition, a repeated measures ANCOVA model may be used to estimate the average treatment effect over the first 12 months and 24 months.

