- Any Grade 4 drug-related AE or laboratory abnormality (including but not limited to creatinine, AST, ALT, or total bilirubin), except for the following events that do not require discontinuation:
 - Grade 4 neutropenia ≤ 7 days
 - Grade 4 lymphopenia
 - Isolated Grade 4 electrolyte imbalances/abnormalities that are not associated with clinical sequelae and are corrected with supplementation/appropriate management within 72 hours of their onset
 - Grade 4 drug-related endocrinopathy AEs, such as, hyper- or hypothyroidism, or glucose intolerance and adrenal insufficiency, that resolve or are adequately controlled with physiologic hormone replacement (corticosteroids, thyroid hormones) or glucose-controlling agents, respectively, may not require discontinuation after mandatory discussion with and approval from the study medical monitor/designee.
- Grade 3 or 4 hypersensitivity reaction or infusion reaction. Please refer to Section 5.9 on Treatment of Related Infusion Reactions
- Any event that leads to delay in dosing lasting > 8 weeks (2 or more consecutive IV drug cycles missed) from the previous dose requires discontinuation, with the following exceptions:
 - Dosing delays to allow for prolonged steroid tapers to manage drug-related AEs are allowed.
 - Dosing delays lasting > 8 weeks (2 or more consecutive IV drug cycles missed) from the previous dose that occur for non-drug-related reasons may be allowed if approved by the study medical monitor/designee.

Prior to re-initiating treatment in a participant with a dosing delay lasting > 8 weeks (2 or more consecutive IV drug cycles missed), the study medical monitor must be consulted. Tumor assessments should continue as per protocol even if dosing is delayed. Periodic study visits to assess safety and laboratory studies should also continue every 6 weeks or more frequently if clinically indicated during such dosing delays.

• Any AE, laboratory abnormality, or intercurrent illness that, in the judgment of the investigator, presents a substantial clinical risk to the participant with continued IV study drug dosing.

Please refer to Appendix 8: AE Criteria for Delay, Resume and Discontinue of Nivolumab.

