- ^a = The study visit window in the treatment phase is ± 3 days, unless noted otherwise for a particular assessment. Study visits should take into account the subject's investigational product supply. Only 1 cycle of oral study drug will be dispensed to the subject on Day 1 of each cycle.
- b = First dose of oral study drug in Cycle 1 should be administered within 3 days of enrollment/randomization. Study treatment continues in 28-day cycles (± 3 days) until 24 months after initiation of oral/IV combination study treatment, disease progression, or unacceptable toxicity, whichever happens first.
- e Patients must be followed for at least 5 months after last IV dose of study treatment. Safety Follow-up Visit 1 (SFU1) should occur 28 days (±7) from the last dose of study drug (oral or IV, whichever is later) or can be performed on the date of discontinuation if that date is at least 28 days from last dose. Safety Follow-up Visit 2 (SFU2) occurs approximately 5 months (±7) from last IV dose of study drug. Chemistry and hematology are only necessary at SFU2 if toxicities are present. Both follow up visits should be conducted in person. If a patient remains on oral study drug after discontinuation of IV study drug, the 5-month Safety Follow-up Visit can be performed at a cycle visit, provided it has been at least 5 months since the last IV dose.
- d = Consent may be completed outside the 120-day screening window as consent does not expire. Reconsent is not required if outside the screening window. The screening period begins with the first study-specific procedure, performed outside standard of care, and only after consent for study participation has been provided.
- e Patient's medical record must include prior treatments received, dates of administration, date of progression and how assessed, and radiology reports. BRCA1/2 mutation status and if germline or somatic, if known, will also be recorded on the appropriate eCRF. Medical history should be updated within 3 days of the first dose of study drug.

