- Tumor scans to be performed every 12 calendar weeks (a 7-day window prior is permitted) relative to Cycle 2 Day 1 (C2D1) for the first 3 years and every 24 weeks thereafter until objective radiological disease progression. Disease progression will only be determined by RECIST v1.1. Patients with a CR at study entry will only be considered to have disease progression if a new lesion is identified. Patients who meet GCIG CA-125 criteria for disease progression should have a radiologic assessment and be assessed by RECIST v1.1. If the radiologic assessment does not confirm disease progression, patients should continue on treatment and continue to be assessed by RECIST v1.1 per the protocol schedule of assessments.
- 1 = To be performed every 12 weeks (within 7 days prior is permitted) relative to C2D1 for the first 3 years and every 24 weeks thereafter until investigator-assessed radiologic disease progression by RECIST v1.1 or initiating subsequent anticancer treatment for any patient who discontinued from study treatment for reason other than disease progression or death. Tumor scans at the End-of-Treatment Visit are only required if it has been 12 weeks or more since the last scan.
- m = The TOI FACT-O and EQ-5D-5L assessments must be completed prior to other scheduled study procedures and dosing (if applicable) at Screening, on Day 1 (Cycle 1 through 3, and Cycle 5), then every 12 weeks (aligning with CT scans) until treatment discontinuation. In addition, PRO assessments will be performed at the End-of-Treatment Visit, at the SFU1 (28-day post-treatment discontinuation) and the SFU2 (5-month post-IV treatment discontinuation) for all patients.
- ⁿ = Includes RBC and parameters (Hgb, Hct, MCV, MCH, MCHC) and reticulocyte count, WBC and differential (with ANC), and platelet count. Blood will be analyzed by a central laboratory. A duplicate sample may be collected and analyzed by the local laboratory for immediate eligibility/treatment decisions.

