7.4.4 Day 1 of Cycles 3 and Beyond

The following procedures will be completed:

- Physical examination;
- Weight;
- Vital signs;
- Concomitant medications and procedures;
- Disease assessment/tumor scans every 12 calendar weeks (within 7 days prior is permitted) relative to C2D1 for the first 3 years and every 24 weeks thereafter until objective radiological disease progression;
- PRO, using the TOI FACT-O and EQ-5D-5L instruments or other format, as appropriate, at Cycle 3, Cycle 5, and then every 12 weeks, to coincide with disease assessment/tumor scans (perform before other assessments that day) until treatment discontinuation or until the data cut-off for the primary analysis, whichever comes first;
- ECOG performance status (Appendix 3);
- Hematology;
- Serum chemistry (fasting is not required);
- CA-125 measurement;
- Blood sample for ctDNA analysis (Day 1 of Cycle 1 through Cycle 6, and at the same time as radiological imaging thereafter);
- PK samples for nivolumab prior to the IV infusion at Cycle 6 and every 4 cycles thereafter while IV study drug continues (see Table 6 and Section 7.5.6);
- Immunogenicity sample for nivolumab prior to the IV infusion at Cycle 6 and every 4 cycles thereafter while IV study drug continues (see Table 6 and Section 7.5.6);
- Administration of IV study drug;
- AE monitoring;
- Plasma PK samples for rucaparib (prior to the first dose of study drug taken this day; Cycle 3 and Cycle 4 only; see Section 7.5.6).

Oral study drug (rucaparib or placebo) will be dispensed to the patient in sufficient quantity to last until the next clinic visit; for Cycles 3 and 4, oral study drug can be resumed after the PK sample is collected. Patients may take study drug with or without food. Patient will record dosing information in their dosing diary.

Patients will continue dosing with study drug at home with or without food, taking doses BID at about the same times every day. Patients will record dosing information in their dosing diary.

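### After Cycle 5 the quality-of-life forms follow the 12-week scan calendar, but the ATHENA-COMBO visit windows follow cycle dates and leave 41-day gaps, so some validly collected forms can have no visit

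*SAP*

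**What the plan says.** **Collection.** The COMBO SAP (10.3.6) has FACT-O completed at screening and on Day 1 of Cycles 1 to 3 and 5, "then every 12 weeks (aligning with CT scans) until treatment discontinuation". Protocol 7.4.4 agrees: after Cycle 5 the forms come "and then every 12 weeks, to coincide with disease assessment/tumor scans (perform before other assessments that day").

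**Scan calendar.** Protocol 7.4.4 sets "Disease assessment/tumor scans every 12 calendar weeks (within 7 days prior is permitted) relative to C2D1 for the first 3 years". Protocol 5.6.4.2 adds "Tumor assessments should continue as per protocol even if dosing is delayed", and 5.6.4.1 says the same for the oral drug.

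**Cycle dates.** Table 5, footnote b: "Study treatment continues in 28-day cycles (± 3 days) until 24 months after initiation of oral/IV combination study treatment".

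**Analysis windows.** COMBO SAP Table 3 uses the recorded cycle dates. The Cycle 5 window closes at "EDC Cycle 6 Day 1 date + 7 days" and the next opens at "EDC Cycle 8 Day 1 date -7 days". The pattern repeats every three cycles. If several forms fall in one window, the closest to the visit date is used. Nothing is said about a form that falls in no window. Section 10.3.7 applies the same table to EQ-5D-5L, and the MONO SAP (10.3.3) has the same windows.

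**The concern.** Collection and analysis run on different clocks. They agree only while cycles stay on the 28-day grid. When a patient's cycles lag the calendar, a form completed on its scan date can fall before its window opens. It then has no visit and cannot enter the per-visit ANCOVA of FACT-O or EQ-5D. That sits badly with the SAP's general convention (section 3) of using all available data as far as possible.

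The forms at risk belong to patients whose cycles have slipped. If slips reflect toxicity, the missing forms are not a random subset in a comparison that speaks to tolerability. The loss could also go unseen: the MONO SAP (10.3.5) reports form completion by window, and the COMBO SAP has no such section.

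**Working it through.** **Inputs.** 28-day cycles, ±3 days (Protocol Table 5, footnotes a and b; 5.5.1). Scans every 84 days from Cycle 2 Day 1 (C2D1), up to 7 days early (Protocol 7.4.4). Window limits from COMBO SAP Table 3. Days are counted from C1D1 = 0.

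**1. The plan's own figure.** Scan k falls on day 28 + 84k, giving days 112, 196 and 280, or Weeks 16, 28 and 40. These match the scan weeks in the MONO SAP's Figure 1. Cycle j Day 1 falls on day 28(j − 1), so Cycles 5, 8 and 11 start on the same three days. On exact 28-day cycles every form is in its window.

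**2. Gaps.**
- Cycle 3 window: 56 − 3 = 53 to 84 + 7 = 91.
- Cycle 5 window: 112 − 7 = 105 to 140 + 7 = 147.
- Cycle 8 window: 196 − 7 = 189 to 224 + 7 = 231.
- Uncovered between Cycles 3 and 5: 105 − 91 − 1 = 13 days.
- Uncovered between Cycles 5 and 8, and between every later pair: 189 − 147 − 1 = 41 days.
- Covered per 84 days: 147 − 105 + 1 = 43. Uncovered share: 41/84 = 48.8%.

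**3. The slip that loses a form.** Take the Week 28 form, completed e days before day 196, with Cycle 8 Day 1 late by s days.
- It is in the Cycle 8 window if 196 − e ≥ 189 + s, that is, s ≤ 7 − e.
- If the slip arose before Cycle 6 Day 1, the Cycle 5 window closes at 147 + s. The form falls there if s ≥ 49 − e.
- If the slip arose between Cycle 6 Day 1 and Cycle 8 Day 1, the Cycle 5 window still closes at 147, and every s above 7 − e leaves the form without a visit.

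| Scan | Kept as Cycle 8 | No visit | Labelled Cycle 5 |
|---|---|---|---|
| On date, slip before Cycle 6 | 0–7 days | 8–48 days | 49 or more |
| 7 days early, slip before Cycle 6 | 0 days | 1–41 days | 42 or more |
| On date, slip after Cycle 6 | 0–7 days | 8 or more | never |

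**4. How often.** The documents give no frequency or length of cycle slips, so these are ranges under stated assumptions.
- *Form done at the nominal Day 1 visit:* loss near 0.
- *±3 days not accumulating, scans on date:* the lag is at most 3 days, so loss is 0%. With scans spread evenly over 0 to 7 days early it is about 11%.
- *±3 days accumulating at random without trend, scans on date:* each cycle's deviation, uniform on −3 to +3 days, has variance (9+4+1+0+1+4+9)/7 = 4. The lag at Cycle x therefore has standard deviation √(4(x − 2)), or 4.9, 6.9 and 9.8 days at Cycles 8, 14 and 26. Simulating the chance of a lag of 8 to 48 days gives about 6%, 14% and 22%. As a check, the normal approximation at Cycle 8 has z = 7.5/4.9 = 1.53, an upper tail of 6%.
- *As above, scans spread evenly over 0 to 7 days early:* about 23%, 29% and 35%. With every scan 7 days early: 46% to 48%.
- *Steady drift, scans on date:* +1 day per cycle loses the forms from Week 40 on; +2 days per cycle loses them from Week 28 on.

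**The case against.** **Forms may be done at Day 1 visits.** Protocol 7.4.4 lists the 12-weekly form under cycle Day 1 procedures, and after Cycle 2 the scheduled treatment visits are Day 1 only. A form completed at Cycle 8 Day 1 is kept however late that visit is. This stands, and it is why the range starts near 0. It does not remove the conflict, because the same section ties the form to the scan calendar.

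**Holds need not move cycle dates.** A reader might infer that a toxicity hold pushes all later cycles back by a full cycle, so that every later form is lost. The documents do not support this as the usual case. Protocol 5.6.1.2 and 5.6.2.2 have the IV drug resume at the next scheduled timepoint, and the two drugs can be held separately (5.6). Not every hold shifts the recorded dates.

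**The allowance may not accumulate.** Protocol 7.1 can be read as ±3 days around a fixed scheduled time; 5.5.1 reads as an allowance on each cycle's length. The text does not settle it, so 0% belongs in the range.

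**Arm bias.** A reader might infer that the loss makes the combination look better tolerated. No delay rates by arm are given, Arms A and B both take rucaparib, and the delay rules apply to placebo as well. A difference between arms is possible, but neither its size nor its direction can be computed.

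**The forms are not wholly discarded.** The final-visit analysis does not use these windows, and the SAP does not say that unassigned forms are dropped. It simply gives them no visit.

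**Conclusion.** The mismatch is real and follows from the text alone: collection on a fixed 12-week calendar, assignment by movable cycle dates, a 7-day early margin, 41-day gaps, and no rule for a form in a gap. It bites from Cycle 8 on, since the Cycle 5 form is itself due on a cycle Day 1.

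Its size depends on site practice and on how the visit allowance is read. It runs from near 0 to about 6%, 14% and 22% at Cycles 8, 14 and 26 with random accumulation and scans on date, and higher with early scans or systematic drift. None of these is an estimate of what happened in the trial.

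FACT-O and EQ-5D are exploratory and outside multiplicity control. The final-visit analysis is unaffected, and no primary or key secondary result changes. The point is minor, but worth correcting because it is cheap and the forms already exist.

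**What to change.** Keep the C2D1 and C3D1 windows. Replace the later ones with contiguous, non-overlapping calendar windows on the scan schedule:

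- Targets at Weeks 12, 24, 36 and so on from C2D1, or from C1D1 + 28 days if C2D1 did not occur. The latter agrees with Protocol 7.5.3.1, which puts the first scan 16 weeks after C1D1 in that case (28 + 84 = 112 days).
- Start the Week 12 window the day after the Cycle 3 window closes (C4D1 + 7 days, nominally day 63 after C2D1). A plain ±6 weeks would open on day 84 − 42 = 42 and overlap the Cycle 3 window by about three weeks.
- Set later boundaries midway between targets, with each boundary day in one window only.
- Assign each on-treatment form to the nearest target, and use the same windows for EQ-5D in 10.3.7.

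**Cost.** SAP wording and programming; no new data. Some forms will sit further from their nominal week. The windows will differ from those in the MONO SAP, whose comparison also uses Arm B; showing the current Table 3 windows as a sensitivity display covers this.

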## 3 GENERAL ANALYSIS CONVENTIONS

Efficacy analyses will be analyzed in the ITT Population as described in Section 10 below.

All safety analyses will be based on the Safety Population, which consists of all patients who received at least 1 dose of protocol-specified treatment of oral study drug and/or IV study drug. Further, for safety analyses, patients randomized to either arm containing IV Nivolumab (ie, Arm A or Arm C) who never receive Nivolumab, will be analyzed in the analogous arm containing IV Placebo (ie, Arm B or Arm D, respectively).

Quantitative variables will typically be summarized using frequencies and percentages for appropriate categorizations and may also be summarized using descriptive statistics. For variables summarized with descriptive statistics, the following will be presented: N, mean, standard deviation, median, minimum, and maximum. Categorical variables will be presented using frequencies and percentages.

The Kaplan-Meier methodology will be used to summarize time-to-event variables. The 50th (median) percentile with the 95% CI will be summarized for each randomized treatment group. The stratified hazard ratio from the Cox proportional hazards model will be used to estimate the HR between the randomized treatment groups. The number of patients with events and the number of censored patients will also be presented.

The primary endpoint of invPFS, secondary endpoint of OS, bicrPFS (if applicable), ORR and exploratory analyses for the ITT population will be analyzed using the stratification factors of HRD classification, disease status, and timing of surgery. If the model does not converge or if there are only patients from a single treatment arm per stratum or if one or more of the strata contain few patients (eg, <5 patients) then the stratification factor of disease status will be omitted first, then timing of surgery, if necessary. Additionally, the Firth correction in the PHREG procedure will be used.

All data will be used to the maximum possible extent but without any imputations for missing data.

Baseline is defined as the last measurement on or prior to the first day of oral study drug administration or randomization date if the patient was never treated.

Results of all statistical analysis will be presented using 95% CIs and two-sided p-values. The significance level for ATHENA-COMBO is set at a one-sided p=0.0125 (two-sided p=0.025).

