#### 10.3.7 Patient Reported Outcome of EQ-5D

Analyses of changes and/ or percent changes from baseline will be analyzed for each scheduled postbaseline visit and for the final visit for the EQ5D instrument and the EQ VAS. Patients who do not have both a baseline measurement and at least one postbaseline measurement will not be included.

The final visit is defined as the last assessment within 28 days after date of last dose of oral study drug or within 5 months of last IV study drug, whichever is later. For the protocol-specified post-baseline visits; the EQ-5D-5L assessment will be grouped in actual scheduled visit windows as described in Table 3. If more than one assessment date falls within a given visit window, the one that is closest to the actual scheduled EDC visit date will be used. In the case of ties, the assessment prior to the scheduled visit date will be used. The data sets should highlight the value for the patient that was included in the summary table, wherever feasible. The summary tables and graphs will only display data if the number of observations is greater than 10 in each treatment arm.

At a given visit, the change from baseline will be analyzed for the treatment comparisons using an Analysis of Covariance (ANCOVA) with treatment and stratification variables as categorical factors and baseline measurement for the parameter as a continuous covariate. In addition, a graphical presentation of mean changes over time may be presented.

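### The COMBO quality-of-life comparisons rest on separate per-visit ANCOVAs among patients essentially still on treatment, so late-visit arm differences are at risk of bias from score-related drop-out; the direction is not known in advance and the size is small to moderate

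*SAP*

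**What the plan says.** **Firm analysis.** COMBO SAP section 10.3.6 (FACT-O) states: "At a given visit, the change from baseline will be analyzed for the treatment comparisons using an Analysis of Covariance (ANCOVA". The model holds treatment, the stratification variables and the baseline score. Section 10.3.7 repeats this for EQ-5D.

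**Longitudinal model.** For FACT-O, "a repeated measures ANCOVA model may be used to estimate the average treatment effect over the first 12 months and 24 months"; no covariance structure or missing-data assumption is given. For EQ-5D there is none, and the paragraph closes with an optional graph: "In addition, a graphical presentation of mean changes over time may be presented".

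**Who contributes.** Questionnaires are taken at the early cycles, "then every 12 weeks (aligning with CT scans) until treatment discontinuation". The visit windows in 10.3.6 are built on recorded cycle dates. Off treatment, "PRO assessments will be performed at End of Treatment, and at the FU1 (28-day Safety Follow-up) and the FU2 (5-month Safety Follow-up) for all patients". A final-visit analysis is also planned: "The final visit is defined as the last assessment within 28 days after date of last dose of oral study drug", or within five months of the IV drug if that is later.

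**Missing data.** "Patients that do not have both a baseline measurement and at least one postbaseline measurement will not be included" (10.3.6). Section 3 adds: "All data will be used to the maximum possible extent but without any imputations for missing data".

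**Status.** Section 10.3 treats these endpoints as exploratory, without multiplicity adjustment. The COMBO SAP plans no PRO completion tables and no PRO missing-data sensitivity analysis. The MONO SAP plans completion and disposition tables in its section 10.3.5.

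**The concern.** Scheduled-visit comparisons contain essentially the patients still on treatment, and that group shrinks over two years. An ANCOVA fitted at one visit uses the baseline score and strata but ignores what the patient reported in between. If patients who report worse scores are more likely to stop, those who remain are a selected group. The selection need not cancel between arms if the arms lose patients at different rates, if stopping is tied to scores more closely in one arm, or if treatment itself shifts scores.

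At stake is how the late-visit HRQoL contrasts between the combination and rucaparib alone are read. These are the visits where cumulative treatment burden would show. Leaving the longitudinal model optional, with two averaging periods and no covariance structure, also leaves its use to be decided after the data are seen.

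**Working it through.** The documents give no SD, power or drop-out figure for HRQoL, so there is no planned figure to reproduce. The check has four steps. Score SD, correlations and the strength of the score–drop-out link are assumptions throughout.

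**1. How many remain at late visits.** Inputs: planning median PFS of 28 months (Arm A) and 20 months (Arm B) from COMBO SAP 2.4, and 28-day cycles. Counting progression only, the share on treatment at month t is 2^(−t/median), with t = (cycle − 1) × 28/30.4375.

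| Visit | Month | Arm A | Arm B |
|---|---|---|---|
| C8 | 6.4 | 85% | 80% |
| C14 | 12.0 | 74% | 66% |
| C20 | 17.5 | 65% | 55% |
| C26 | 23.0 | 57% | 45% |

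At C26: 2^(−23.0/28) = 0.566 and 2^(−23.0/20) = 0.451.

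**2. Bias with no true difference.** Simulation: 400 per arm (SAP 2.3), 400 replicates, scores with SD 1, within-patient correlation 0.6 + 0.4·exp(−gap in months/6), visits C2 to C26. The stopping hazard is multiplied by exp(−g × last observed score). Per-visit ANCOVA with baseline is compared with a likelihood-type repeated-measures fit (unstructured, missing at random). The SE of one trial's estimate at C26 is 0.08 to 0.09 SD, so simulation error on each mean is about 0.083/√400 = 0.004.

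| Drop-out (medians A/B) | ANCOVA bias at C26, SD | Repeated-measures fit |
|---|---|---|
| Unrelated to score (28/20) | −0.003 | 0.000 |
| Score-related, same in both arms (20/20, g = 0.5) | −0.004 | −0.004 |
| Score-related, A stays longer (28/20, g = 0.5) | −0.029 | −0.005 |
| Same, stronger link (g = 1) | −0.041 | −0.001 |
| Score-related, A stops more (15/20, g = 0.5) | +0.033 | +0.006 |
| Link differs by arm (20/20, g = 0.8 in A, 0.2 in B) | +0.114 | +0.008 |
| Driven by the unobserved current score (28/20, g = 0.5) | −0.036 | −0.015 |

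There is no bias in the first two rows. In the others the sign depends on which arm loses more low scorers. In the last row the model removes (0.036 − 0.015)/0.036 = 58% of the bias.

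**3. Bias with a true difference.** Separate runs assumed SD 15, with drop-out depending on the last observed score unless stated. All figures are in points.

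- True −2, Arm A stopping more: ANCOVA −1.22 with a moderate score link; −0.57 and −0.54 in two runs with a strong link.
- True −2, Arm A staying longer: ANCOVA −2.39.
- True −2, same drop-out rule in both arms: −1.84 and −2.03 in two runs with a moderate link, −1.78 with a strong link.
- True −5, same rule, strong link: ANCOVA −4.29, missing-at-random fit −5.05.
- For a true −2 the missing-at-random fit gave −1.86 to −2.13 across these runs, but only −1.51 when drop-out depended on the unobserved score.

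So an identical drop-out rule does not fully protect the ANCOVA when there is a real effect, because the worse-feeling arm then loses more low scorers. The shrinkage is mild: 4.29/5 = 86% retained in the strongest case tried.

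**4. Size in points.** For an assumed TOI SD of 12 to 18, step 2 gives 0.029 × 12 = 0.3 to 0.114 × 18 = 2.1 points. Step 3, for a true −2, gives departures from about zero up to 2 − 0.54 = 1.46 points. MONO SAP 10.3.3 takes 10 points on the TOI as clinically relevant.

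**The case against.** **The bias is conditional.** A reader might infer that every late-visit difference is biased. The documents do not support that, and step 2 shows no bias when stopping is unrelated to scores, or related to them in the same way in both arms with no true effect. This stands.

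**The direction is open.** A reader might also infer that the plan understates harm from the combination, because nivolumab adds its own discontinuations. That needs Arm A to leave treatment sooner, and no document says it will. The planning medians point the other way, and under them the ANCOVA error goes against the combination. Protocol 5.6.4 also lets the two drugs be stopped independently, so stopping the infusion alone need not end questionnaires. This stands too.

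**Off-treatment assessments exist.** They do, and the final-visit analysis brings back some patients who have stopped. But it pools assessments taken at very different times, and the safety follow-up assessments have no cycle window of their own. Neither corrects a contrast at a given cycle.

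**The choice is partly one of target.** Per-visit ANCOVA describes patients still treated; a mixed model estimates scores as if patients had stayed on treatment. That is fair, and the target should be stated. But a difference between two selected groups is not a randomised comparison, and the SAP presents it as the treatment comparison.

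**The simulations favour the model.** Most let drop-out depend on observed scores, which is the model's own assumption. The runs that break it show only partial correction.

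**Little depends on it.** The endpoint is exploratory and the sizes are well below 10 points. That limits the priority of the point but does not make the planned method the better one.

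**Conclusion.** The concern holds in conditional form. Under COMBO SAP 10.3.6 and 10.3.7, late-visit HRQoL differences are at risk of bias when drop-out depends on earlier on-study scores and either drop-out differs by arm or treatment has a real effect. The sign is undetermined.

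Under the assumptions tried, the size is up to about 2 TOI points, which is small to moderate. It rests on assumed SDs, correlations and score–drop-out links, since the documents give none. No confirmatory conclusion is affected. The case for change is that a better-specified method is available at little cost, not that a key result is in danger.

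**What to change.** In the COMBO SAP, 10.3.6 and 10.3.7:

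- Make a mixed model for repeated measures the stated analysis for FACT-O TOI and EQ-5D. Terms: treatment, visit, treatment-by-visit, baseline, baseline-by-visit and strata, with unstructured covariance.
- Take the visit-level contrasts and the 12- and 24-month averages from that model.
- State that it targets scores as if patients had remained on treatment and assumes missing at random.
- Keep the per-visit ANCOVA as supportive.
- Add one missing-not-at-random sensitivity analysis.
- Report PRO completion by arm and visit, as MONO SAP 10.3.5 does.

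The cost is SAP wording, one model per instrument, one sensitivity analysis and a completion table, all on data already collected. The downside is reliance on missing at random: if stopping depends on scores never observed, the model removes only part of the bias.

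MONO SAP 10.3.3 and 10.3.4 have the same structure, but the sponsor team was unblinded to Arms B and D on 23 March 2022 (COMBO SAP 3.5). There the model could serve at most as a supplementary analysis, labelled as added after unblinding.
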